25. Any subject who has been enrolled in any previous clinical study with inhaled NO administered through pulse delivery.

Additional Criteria to Continue to Treatment Phase from Run-in period (Week 0 to Week 2)

1. Subjects must demonstrate an average daily usage of the INOpulse device of ≥ 12 hours (rounded to the nearest hour), with no more than 2 days of usage < 8 hours per day, during the initial 2 weeks of study.
2. If a subject experiences clinical worsening during the Screening or Run-in period, the subject will not be eligible to enter into the treatment phase of the study.
3. Subjects who have been randomized at baseline and found not to meet all Inclusion criteria and/or who meet Exclusion criteria during the Run-in period will be withdrawn from the study. These subjects will be replaced to meet total target enrollment.

Part 2 Open Label Period: Diagnosis and main criteria for inclusion and exclusion:

Inclusion Criteria Part 2:

1. Informed Consent Form prior to the initiation of any study mandated procedures or assessments
2. Subject must have completed 18 weeks of blinded therapy and all assessments at week 18
3. In the opinion of the Investigator, open label treatment is in the best interest of the subject after 18 weeks of blinded treatment is completed

Exclusion Criteria Part 2 Open Label Period:

1. Subject has initiated therapy with Riociguat

Investigational product, dosage and mode of administration:

Part 1 Blinded Treatment Period:

In a randomized, double-blind manner, all subjects randomized to iNO at a dose setting of 75 mcg/kg IBW/hr will be treated by means of an INOpulse delivery device and product-specific cannula. The active study drug, nitric oxide for inhalation (iNO), will be provided in size 0.074 liter aluminum cartridge at a concentration of 6.0 mg/L (4880 ppm). All subjects will change cartridges approximately every 12 hours.

All subjects randomized to receive iNO will receive 15 mcg/kg IBW/hr for the first 2 weeks (Run-in phase) followed by iNO at 75 mcg/kg IBW/hr for 16 weeks.

Part 2 Open Label Period:

All subjects enrolled in Part 2 Open label treatment will receive iNO at 75 mcg/kg IBW/hr.

Duration of treatment:

Part 1 Blinded Treatment Period:

Until the subject has completed 18 weeks of blinded treatment

Part 2 Open Label Period:

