The results of Part 2 of the study demonstrated that pulsed iNO was well tolerated beyond the initial 16-week treatment period in Part 1. The incidence of Respiratory AEs and related Respiratory AEs in the Part 2 of the study were comparable in both the iNO 75 and iNO 25 treatment groups. No subjects had a MetHb level $\geq 7\%$.

Subjects with LTOT are more likely to be compliant and may have better outcomes. In the Phase 3 trial, recruitment will be limited to only subjects on LTOT.

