8. STUDY DESIGN

8.1. Overall Study Design

This is a multi-center, randomized, double-blind, placebo-controlled, parallel-group design to determine the efficacy, safety and tolerability of pulsed iNO versus placebo in symptomatic subjects with PAH currently receiving background PAH medication and LTOT.

All subjects will be treated by means of a blinded INOpulse delivery device. The device measures daily exposure (minutes per day in use, measured as breath detection).

The study consists of two parts Part 1, the Blinded Treatment Period, and Part 2, the Open Label Extension Period. After the Screening period, the subjects will be randomized at Week 0 then enter a double-blind, Run-in period (Week 0 to Week 2) to assess their eligibility to continue in the study by their usage of the INOpulse device for an average ≥ 12 hours (rounded to the nearest hour) per day with no more than 2 days of usage < 8 hours per day. All subjects will be analyzed for safety during this Run-in period. Those subjects not meeting the 12 hour INOpulse device usage requirement (by Week 2) will be discontinued and ineligible to proceed to the next phase of treatment. Subjects meeting the device usage requirement, and all Inclusion/Exclusion criterion (by Week 2), will qualify to enter into the next phase of treatment.

Subjects who are unable to meet enrollment criteria during the Run-in period may be rescreened at the discretion of the Sponsor.

Subjects will be randomized to a treatment assignment as described in [Table 1](#) below. Subjects randomized to active iNO will receive a reduced dose of iNO during run in and subjects randomized to placebo will receive placebo during run in.

At Baseline, all subjects will be stratified for prostanoids usage.

LTOT flow rates should be kept constant throughout the study unless the subject has persistent desaturations to less than 88% of SpO₂, or otherwise clinically indicated. LTOT flow rate with the estimated length of use per day must be documented in the eCRF at all visits. Subjects will be encouraged to use their oxygen during the day and night as prescribed by their treating physician. All 6MWTs will be performed while subjects are receiving oxygen and carrying the INOpulse device (including baseline assessments).

Additional specific PAH therapies may be added only for evidence of clinical worsening due to PAH as defined in the protocol throughout the trial.

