- Pregnancy test
- Survival status
- All blinded drug cartridges from Part 1 of the study must be returned to the site or Sponsor.

Assessments Part 2

Part 2 Week 0 Visit: The following Assessments will be performed:

- Informed Consent
- Methemoglobin via pulse oximetry (O₂ flow rate)
- Drug Device Dispensation for Open Label treatment
 - If the subject continues to participate, at this visit the subject will be dispensed a 1 week supply of study drug. Additional supplies will be delivered directly to the subject's home every 4 weeks. The used cartridges must be returned and will be picked up from the subject's home when the new supplies are delivered.

- Pregnancy test (at the discretion of the investigator)
- Evaluation for symptomatic Rebound Hypertension while under medical supervision, after start of study drug and prior to sending the subject home as described in [section 11.1.15](#)

Part 2 Week 2 Visit is a Telephone Visit:

Study Staff will contact the subject via telephone call and the following assessments will be completed:

- Review of prior and concomitant medications
- Assessment of AE,SAEs, AESI

Part 2: Week 16, Week 32, and Week 52 Visits - the following assessments will be performed:

- Prior and concomitant medications
- WHO Functional Class
- Conduct 6 Minute Walk Test
- Borg Dyspnea Scale
- Laboratory – Hematology and Chemistry (Week 52 only)
- Pregnancy test (at the discretion of the Investigator)
- Vital Signs including HR, RR, BP and temperature. SpO₂ and methemoglobin (Week 52 only) via pulse oximetry (O₂ flow rate)
- Assess AEs, SAEs. AESIs
- Drug Device Dispensation (every 4 weeks via home delivery)
- Review Drug Device Usage
- Evaluation for symptomatic Rebound Hypertension while under medical supervision, after start of study drug and prior to sending the subject home as described in section 11.1.15

Part 2: Every 4 Month Visits: The following assessments will be performed:

- Prior and concomitant medications
- Assessment of AEs, SAEs, AESI
- Vital signs: BP and HR, SpO₂ and methemoglobin via pulse oximetry (annually)
- Review device usage with the subject
- Laboratory – Hematology and Chemistry will be conducted on a yearly basis (Pregnancy testing will be left to the discretion of the Investigator)
- Drug Device Dispensation (every 4 weeks via home delivery)

Part 2: End of Study (EOS) or Early Discontinuation- The following assessments will be performed:

- Prior and concomitant medications

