11.1.11. Hematology, Chemistry, Methemoglobin, NT-proBNP

Hematology laboratory tests will be performed in Part 1 at Screening and Week 18, and at any time of an early drug discontinuation before Week 18. These laboratory tests will include complete blood count (CBC) with differential and platelet count. In Part 2 will be performed at Week 52, yearly and at End of Study or Early Discontinuation.

Chemistry laboratory tests will be performed in Part 1 at: Screening and Week 18, and at any time of an early drug discontinuation before Week 18.

In Part 2, Hematology and Chemistry laboratory tests will be performed at Week 52, then on a yearly basis until EOS, or Early Discontinuation. These laboratory tests include: electrolytes (Na, K, HCO₃, and Cl), glucose, blood urea nitrogen (BUN), creatinine (Cr), aspartate aminotransferase (AST), alanine aminotransferase (ALT), gamma-glutamyl transpeptidase (GGT), alkaline phosphatase, lactate dehydrogenase (LDH), creatine phosphokinase (CPK), magnesium, bilirubin total/direct, uric acid, total protein, and albumin.

Methemoglobin levels (%) will be measured by oximetry in Part 1 at Screening and Week 2, Week 6 and at any time of an early drug discontinuation before Week 18. In Part 2 will be performed at Week 0, Week 52 and yearly including EOS or early discontinuation

NT-proBNP will be collected in Part 1 at Screening and Week 18. NT-proBNP will not be collected in Part 2

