11.1.15. Evaluation for Symptomatic Rebound Pulmonary Hypertension

In Part 1, after randomization at Week 0 and at end of Run-in, Week 2, all subjects will remain in the hospital or clinic under medical supervision for 1 hour after starting study drug and for 1 hour after study drug is discontinued for observation for signs and symptoms of rebound PH (see [Section 15.1.5](#)). Vital signs, including heart rate, respiratory rate, blood pressure, and SpO₂ will be recorded in the supine position every 15 minutes for 1 hour, and then again every 15 minutes for another hour after discontinuation of study drug.

At Week 0, INOpulse device should be set at 15 mcg/kg IBW/hr. At Week 2 the evaluation will be performed with the INOpulse device reset to 75 mcg/kg IBW/hr

In the opinion of the Investigator, subjects who develop clinically significant signs and/or symptoms consistent with rebound PH (e.g., systemic hypotension, change in heart rate, new onset syncope, or decreased systemic oxygenation) temporally associated with acute withdrawal, and including those associated with device malfunction or failure, will be discontinued from study treatment and not replaced (see [Section 10](#)).

In Part 2 evaluation should be performed at Week 0, Week 16 and Week 32 and Week 52.

During Part 2 if the subject develops clinically significant rebound PH, the subject may continue on open label therapy if it is considered in the opinion of the investigator to be in the subject's best interest.

The final diagnosis of rebound PH will be adjudicated by an ICEC. The DMC will review the data for subjects enrolled in the study and evaluated for rebound PH (including the ICEC adjudication) and make a decision whether or not to continue evaluation for rebound PH and/or to determine additional steps required in order to maintain subject safety.

After the 1 hour observation period off study drug, if the subject's status is unchanged with respect to vital signs and symptoms and subject does not exhibit signs or symptoms of rebound PH, they will restart their blinded study drug treatment and be sent home.

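### Placebo subjects who switch to iNO in Part 2 and stay on it have no scheduled methemoglobin reading between Week 0 and Week 52, whereas Part 1 takes one four weeks after the same setting starts

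*Protocol*

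**What the plan says.** **Exposure.** Under Protocol 8.1, "subjects randomized to placebo will receive placebo during run in", and Table 1 (8.2) keeps that arm on placebo to Week 18. The Synopsis then states: "All subjects enrolled in Part 2 Open label treatment will receive iNO at 75 mcg/kg IBW/hr". No Part 2 run-in is described.

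**Part 1 readings.** Protocol 11.1.15 fixes when the higher setting starts: "At Week 2 the evaluation will be performed with the INOpulse device reset to 75 mcg/kg IBW/hr". Protocol 11.1.11 gives the readings: "Methemoglobin levels (%) will be measured by oximetry in Part 1 at Screening and Week 2, Week 6", plus early discontinuation.

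**Part 2 readings.** The same section continues: "In Part 2 will be performed at Week 0, Week 52 and yearly including EOS or early discontinuation". The visit list in Section 11 agrees, placing "methemoglobin (Week 52 only) via pulse oximetry" on the vital-signs line shared by Weeks 16, 32 and 52. Between Week 0 and Week 16 the only contact is by phone: "Part 2 Week 2 Visit is a Telephone Visit". The Part 2 half of protocol Table 2 and SAP Table 21 show the same schedule.

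**Purpose and reporting.** The primary objective of Part 2 is long-term safety and tolerability (Protocol 6.2.1). SAP 7.3.1 and 9.0 single out placebo-to-active switchers for 6MWD. SAP 9.0 otherwise repeats the Part 1 adverse event tables and does not mention methemoglobin or a safety summary by Part 1 arm.

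**The concern.** One Part 2 schedule serves two groups with different histories. Former iNO subjects who completed Part 1 on drug were read at Week 6, and are read again at Part 2 Week 0 after months at 75. For them a next reading at Week 52 continues a series that already contains on-dose values. For former placebo subjects the Week 6 reading was taken on nitrogen, and the Week 0 reading falls on the day of their first iNO. They enter long-term treatment with no on-dose value, yet follow a schedule that suits subjects who have two.

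What is at stake is the completeness of the safety data in the newly exposed half of a study part whose main purpose is safety. A rise in a switcher who stays on treatment would not be picked up by any scheduled methemoglobin reading during the first year. The primary efficacy result is not touched.

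**Working it through.** No power or alpha figure is involved, and the plan states no figure to reproduce. The check compares visit timings.

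**Inputs**
- Part 1 start of the 75 setting: Week 2, window ±3 days (Protocol 11.1.15; Table 2).
- Part 1 next methemoglobin reading: Week 6, window ±7 days (Protocol 11.1.11; Table 2).
- Part 2 start of the 75 setting for switchers: Week 0, which coincides with Part 1 Week 18 (Table 2, Part 2).
- Part 2 next methemoglobin reading: Week 52, window ±14 days.
- Expected Part 2 entrants: approximately 150 (Table 5, Protocol 12.3).

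**Gap from starting the setting to the next scheduled reading**
- Part 1: 6 − 2 = 4 weeks. With windows: (28 − 7 − 3)/7 = 2.6 weeks to (28 + 7 + 3)/7 = 5.4 weeks.
- Part 2: 52 − 0 = 52 weeks. With the window: (364 − 14)/7 = 50 weeks to (364 + 14)/7 = 54 weeks.
- Ratio: 52/4 = 13. This is a ratio of visit weeks, not of risk.

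**The Week 0 reading.** The documents do not say whether it is taken before or after the supervised dosing. That dosing lasts one hour, so for a switcher the value is either pre-dose or reflects at most about an hour of drug. For a former iNO subject still on treatment the same reading follows 18 − 2 = 16 weeks at 75.

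**On-dose values at 75 held by each group once the Week 0 visit is complete**

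| Part 1 arm | Part 1 Week 6 | Part 2 Week 0 | Next scheduled reading |
|---|---|---|---|
| iNO | 4 weeks at 75 | 16 weeks at 75 | Part 2 Week 52 |
| Placebo | on nitrogen | none, or about 1 hour | Part 2 Week 52 |

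**Contacts inside the gap.** Week 2 is by phone. Weeks 16 and 32 are clinic visits with vital signs, SpO2 by pulse oximetry, a walk test and a supervised rebound evaluation, but no methemoglobin.

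**Number affected.** Assuming entrants split evenly between the Part 1 arms, 150/2 = 75.

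**Effect of using existing visits.** A reading at Week 16 shortens the longest scheduled gap from 52 to 16 weeks. That is still 16/4 = 4 times the Part 1 interval. Part 2 has no clinic visit near four weeks.

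**The case against.** The case for leaving the schedule alone has several parts, and much of it stands.

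- **The documents agree with each other.** The visit list, Table 2, Protocol 11.1.11 and SAP Table 21 give one Part 2 schedule. A reader might infer an internal contradiction. There is none: two study periods are monitored differently, and no reason for the difference is given.
- **The low-dose run-in is not a safety step.** A reader might infer that switchers lose a protective lead-in. Protocol 8.3 ties the run-in to device compliance and to avoiding unblinding by smell, and treats the 15 setting as ineffective. Its absence from an open-label part breaks no stated safety step.
- **The trial is not blind to early rises.** A reader might infer that the extension cannot detect any. Part 1 Week 6 gives early on-dose values in the randomized iNO arm with a placebo comparator. In Part 2 a reading is taken at end of study or early discontinuation, adverse events are assessed at Weeks 2, 16 and 32, and the rebound evaluations record SpO2.
- **There is reassuring precedent.** For the Phase 2 extension the protocol reports (5.1): "No subjects had a MetHb level" of 7% or more. That extension followed a placebo-controlled part and put all its subjects on iNO. The documents do not say how many had switched from placebo or when they were measured, so this supports a light schedule without settling the matter.
- **Methemoglobin is not a named endpoint.** The Part 2 primary endpoint is the incidence of AEs and SAEs.

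What these points leave unanswered is narrow. None of them supplies a scheduled on-dose methemoglobin value, before Week 52, for a former placebo subject who stays on treatment. The protocol itself schedules such a value after the same setting starts in Part 1.

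**Conclusion.** The concern holds as a limited monitoring gap. Switchers who remain on open-label iNO have no scheduled methemoglobin reading from Week 0 until Week 52 (50 to 54 weeks with the window), against 4 weeks (2.6 to 5.4) after the same setting starts in Part 1. Former iNO subjects enter with on-dose values from Part 1 Week 6 and Part 2 Week 0, while switchers enter with none of substance.

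The visit timings come straight from the documents. The figure of about 75 subjects rests on an even split of an approximate 150. No event rate is available, so the number of rises that might go unrecorded cannot be estimated, and the Phase 2 statement suggests that large rises are not expected. The case for change is that the missing information is cheap to obtain in a study part run for safety.

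**What to change.** Reconcile the Part 1 and Part 2 methemoglobin schedules (Protocol Section 11 visit lists, Table 2 and 11.1.11; SAP Table 21) so that newly exposed subjects have an on-dose reading before Week 52, or state why the two parts differ. The Week 16 and Week 32 clinic visits already include pulse oximetry and could carry the reading. This brings the gap to 16 weeks, not to the 4 weeks of Part 1.

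The reading would need to apply to all entrants. Protocol 8.3 keeps Part 1 assignments blinded until the last subject completes 18 weeks, so sites cannot pick out the switchers before then.

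In the SAP, add a Part 2 methemoglobin table split by Part 1 arm. Clarify in the protocol whether the Week 0 reading precedes the first open-label dose.

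Cost: a minor amendment, up to two more non-invasive readings and eCRF values per subject, and one extra table. No dose, threshold or treatment rule is proposed.

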11.1. Details of Study Assessments

11.1.1. Informed Consent

At Screening, each subject (or legally authorized representative) must provide informed consent in writing after having had adequate time to ask questions and consider his/her participation in this study. Consent must be obtained prior to any protocol related procedure or assessment that is not part of the subject's normal care. Subjects will indicate if they are consenting to participate in both parts of the PAH-004 study by checking and initialing Part 1 & Part 2 participation in the ICF. Participating centers will be responsible for assuring that written informed consent is

provided by each subject using an informed consent form (ICF) approved by the Institutional Review Board (IRB) or Independent Ethics Committee (IEC) granting approval for the conduct of the study. Documentation of IRB or IEC approval for the conduct of the study and the ICF must be provided to Bellerophon Pulse Technologies LLC or its designee.

11.1.2. Medical History

At Screening, relevant medical history and demographics (sex, race, and ethnicity) will be assessed.

11.1.3. Prior and Concomitant Medications

All prior and concomitant medications, including all over-the-counter medications, will be recorded in Part 1 at Screening, Baseline, Weeks 2, 6, 10, 14, and 18 including early discontinuation. In Part 2, at Week 2, Week 16, Week 32, Week 52, Every 4 months and Early Discontinuation/End of Study.

11.1.3.1. Diuretic Use

In Part 1 at each study visit, the dose of any diuretic use should be recorded in the eCRF, including spironolactone.

11.1.3.2. PAH Specific Therapies

Specific attention will be paid to PAH specific and supporting therapies. Each dose of any specific PAH therapy should be recorded, including ERA, PDE-5 inhibitor, prostacyclin or a prostacyclin analog. If addition of riociguat is required, the subject will need to be discontinued from study drug, but should remain in study and complete all assessments until EOS. Increases in prostanoid dose may be necessary over the length of the study due to tachyphylaxis and will not be considered a TTCW event. The addition of prostanoid therapy or increases in prostanoid dose as a TTCW event will be determined by the ICEC.

LTOT flow rates should be kept constant throughout the study unless the subject has persistent desaturations to less than 88% of SpO₂, or otherwise clinically indicated. LTOT flow rate with the estimated length of use per day must be documented in the eCRF at all visits.

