7.1.2. Secondary Endpoints

The secondary endpoints include:

1. TTCW, the time (in days) from start of treatment to first event (first day the event is noted), with iNO as compared to placebo, measured from baseline to 18 weeks. TTCW event is defined as any of the following:
 - a. Death (all-cause mortality)
 - b. Atrial septostomy
 - c. Hospitalization due to worsening of PAH (adjudicated)
 - d. Start of new specific PAH treatment (endothelin receptor antagonists [ERAs], phosphodiesterase type-5 [PDE-5] inhibitors or prostanoids), an increase in the dose of an ERA or PDE-5, increase in the dose or frequency of an inhaled prostanoids, or an increase in the dose of an intravenous or subcutaneous prostanoids by >10%.
 - e. Decrease of >15% from baseline or >30% compared with the last study related measurement in 6MWD should be confirmed by a repeat measurement performed at least 14 days later
 - f. Worsening of WHO Functional Class (e.g., from Class II to Class III or IV, OR Class III to Class IV); and should be confirmed by a repeat assessment at least 14 days later
2. Change in WHO Functional Class, with iNO as compared to placebo, from baseline to 18 weeks

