14.1. Allowed PAH Approved Medication Changes During the Study

Currently approved treatments include: synthetic prostacyclin (i.e., epoprostenol, a prostacyclin analog, treprostinil or iloprost), an ERA (i.e., bosentan, ambrisentan, or macitentan), and PDE-5 inhibitors (i.e., sildenafil and tadalafil).

PAH therapies may be altered or additional therapies added only for evidence of clinical worsening due to PAH as defined in the protocol throughout the trial.

LTOT flow rates should be kept constant throughout the study unless the subject has persistent desaturations to less than 88% of SpO₂, or otherwise clinically indicated. LTOT flow rate with the estimated length of use per day must be documented in the eCRF at all visits.

All PAH approved medications should be given as per standard of care, with the exception that inhaled prostaglandins (Ventavis[®] and Tyvaso[®]) and oral sildenafil doses should be not be given within 1 hour of a scheduled RHC.

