15.7. Independent Clinical Events Committee

The members of the ICEC will be experienced clinicians in the care of PAH subjects and experienced in adjudication for clinical trials in PAH. The ICEC will review and adjudicate the following:

- All SAEs
- Rebound PH
- Subject eligibility when eligibility may be unclear

An independent research organization experienced in the adjudication of cardiovascular events will supervise the collection of data on all events. They will maintain a website where the committee members can access the data, determine the need for more data, and record their findings. The research organization will coordinate all ICEC meetings and be responsible for transferring the adjudication data to the Sponsor.

The data presented to the ICEC members will be reviewed and any information that may lead to un-blinding of the reviewer will be removed.

The Sponsor, appointed research organization, and ICEC will create a pre-determined SMQ list to capture all potential event terms that may be reported and attributed to PAH. Once all parties come to agreement on the list, the electronic adjudication system (EAS) will be programmed to identify potential events for adjudication based on the SMQ list. All AEs will be imported into the EAS and compared against the SMQ programmatically. Events will be managed on a daily basis by adjudication staff. Adjudication staff will collect essential elements for review by the ICEC.

An ICEC charter will be developed with input from the ICEC members, the steering committee, research organization and the Sponsor.

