**Table 4: Time Clinical Worsening Event Derivation**

Variables	Module	Source of Data	Derivation	Comments (to be removed later)
All-cause mortality	End of Therapy Status SAE	CRF	One-One mapping	Standard binary field
Atrial septostomy	End of Therapy Status	CRF	One-One mapping	Standard Binary field
Hospitalization due to worsening of PAH (adjudicated)	Adjudication Module	Non CRF	One-One mapping	Standard Field
New PAH treatment	PAH specific therapies	CRF	One-One mapping	Refer to new PAH Therapy Module
Decrease of >15% from baseline or >30% compared with the last study related measurement in 6MWD should be confirmed by a repeat measurement performed at least 14 days later	6 minute walk test	CRF	
1) Decrease of >15% from Baseline
 
Or
 
2) Greater than 30% compared with baseline
 
And
 
3) should be confirmed by repeat
	
Points (1) and (2) are simple derivations ;
 
Point (3) is linked to visit window mapping, so be careful.

Variables	Module	Source of Data	Derivation	Comments (to be removed later)
			measurement performed at least 14 days	
Worsening of WHO Functional Class (e.g., from Class II to Class III or IV, OR Class III to Class IV); and should be confirmed by a repeat assessment at least 14 days later	WHO functional class assessment done at every visit, choose only post baseline	CRF	(1) Class II to class III (2) Class III to class IV (3) Confirmation by repeat assessment at least 14 days later	Points (1) and (2) are simple derivations ;  Point (3) is linked to visit window mapping, so be careful.

2. Change in World Health Organization (WHO) Functional Class (Table 5 and Table 6) from baseline to 18 weeks

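### The protocol says prostanoid increases for tachyphylaxis are not clinical-worsening events, but the TTCW definitions in the protocol and SAP count them, and neither the ICEC list nor the SAP derivation settles the conflict

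*Protocol*

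**What the plan says.** **Protocol 11.1.3.2 (PAH Specific Therapies)** has two sentences on prostanoids. The first is an exclusion, with no limit on size or route: "Increases in prostanoid dose may be necessary over the length of the study due to tachyphylaxis and will not be considered a TTCW event". The second names who decides: "The addition of prostanoid therapy or increases in prostanoid dose as a TTCW event will be determined by the ICEC".

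**Protocol 7.1.2, TTCW criterion (d)** counts an "increase in the dose or frequency of an inhaled prostanoids, or an increase in the dose of an intravenous or subcutaneous prostanoids by >10" percent. No reason for the increase is asked for, and no adjudication is mentioned. Protocol 16.3.2(d), SAP Table 3 (criterion 4) and SAP 7.4.1 (item iv) repeat the criterion. In all four places, PAH hospitalization is the only component marked as adjudicated.

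**Protocol 15.7** lists what the ICEC reviews: all SAEs, rebound PH, and "Subject eligibility when eligibility may be unclear". Prostanoid changes are not on the list.

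**SAP Table 4** has a row for new PAH treatment. Its module is PAH specific therapies, its source is the CRF, and its derivation is one-to-one mapping, with the comment "Refer to new PAH Therapy Module". Only the PAH hospitalization row uses the Adjudication Module.

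**Protocol 14.1** gives a further rule on background treatment: "PAH therapies may be altered or additional therapies added only for evidence of clinical worsening due to PAH as defined in the protocol".

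**Protocol 16.3.4 and SAP 7.5** test 6MWD first, TTCW second and WHO Functional Class third, and stop at the first non-significant result.

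**The concern.** An endpoint inside the type I error hierarchy needs one event definition. Here the passages give opposite answers for the same patient, and the choice falls to whoever programs the endpoint.

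A rise in prostanoid dose for tolerance reflects the background drug rather than worsening disease, so it would be expected at similar rates in both arms. Events of that kind add to the count but carry no treatment signal. They dilute the TTCW hazard ratio, and a failed TTCW test also closes the test of WHO Functional Class. The SAP's separate log-rank analysis of time to PAH specific therapy (Table 26) has the same ambiguity. Stratifying the log-rank test by prostanoid use does not remove these events, because they occur within the prostanoid stratum.

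**Working it through.** **1. The passages applied to one patient.** Take a stable subject on a subcutaneous prostanoid whose dose is raised 15% for tolerance.

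| Place | Result |
|---|---|
| Protocol 11.1.3.2 | Not an event; prostanoid changes are for the ICEC to determine |
| Protocol 7.1.2(d), 16.3.2(d) | Event: 15% > 10% |
| SAP Table 3, 7.4.1(iv) | Event: 15% > 10% |
| Protocol 15.7 | Dose change not listed for ICEC review |
| SAP Table 4 | CRF source, no ICEC input; no reference dose or >10% calculation given |
| Protocol 14.1 | Tolerance is not a listed reason to alter PAH therapy |

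Two boundaries follow. An intravenous or subcutaneous rise of 10% or less is not an event under any passage. Any inhaled increase in dose or frequency is an event under criterion (d), with no threshold.

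**2. Is there a TTCW figure to reproduce?** No. The documents give no TTCW event rate, hazard ratio, event count or power. The power statements in Protocol 16.2 and SAP 5.4 concern 6MWD.

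**3. Illustration A: assumed rates, unstratified.** Inputs from the documents are 75 per arm (SAP 5.4), 1:1 allocation and one-sided 0.025. Assumptions are exponential event times, an 18-week placebo risk of true worsening of 20%, a true hazard ratio of 0.50, and a titration risk q averaged over all subjects and equal in both arms.

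- Hazards over 18 weeks: placebo λc = −ln(0.80) = 0.2231; iNO λt = 0.1116; titration λn = −ln(1 − q).
- Observed HR = (λt + λn)/(λc + λn).
- Events D = 75 × [(1 − e^−(λc+λn)) + (1 − e^−(λt+λn))].
- Power = Φ(√(D/4) × |ln HR| − 1.96).

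For q = 10%, λn = 0.1054. HR = 0.2170/0.3285 = 0.66, D = 75 × (0.280 + 0.195) = 35.6, and power = Φ(1.238 − 1.96) = 24%.

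| q | Events | HR | Power |
|---|---|---|---|
| 0 | 22.9 | 0.50 | 38% |
| 5% | 29.3 | 0.59 | 29% |
| 10% | 35.6 | 0.66 | 24% |
| 20% | 48.3 | 0.75 | 17% |

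Over placebo risks of 10–30% and true hazard ratios of 0.4–0.6, q = 10% lowers power from a range of 14–74% to a range of 8–54%.

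**4. Illustration B: assumed rates, stratified by prostanoid use.** Assumptions are 188 subjects, true worsening 25% on placebo and 12.5% on iNO, and 40–60% of subjects on prostanoids. The titration risk r applies only to prostanoid users and is equal in both arms. Hazards are −ln(0.75) = 0.288 and −ln(0.875) = 0.134, so the true HR is 0.46. The stratified log-rank power uses information D/4 per stratum at one-sided 0.025.

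| r | HR in prostanoid stratum | Power |
|---|---|---|
| 0 | 0.46 | 63% |
| 2% | – | 60–61% |
| 5% | – | 55–58% |
| 10% | 0.61 | 49–53% |
| 20% | 0.70 | 40–46% |
| 40% | 0.81 | 28–35% |

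With 150 subjects and the nominal final level of 0.0229, the r = 0 power is 52%, falling to 40–43% at r = 10%.

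Every scenario tried moves in the same direction. The size depends entirely on the assumed rates.

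**The case against.** **Read together, the passages might be reconciled.** 11.1.3.2 could be taken as a carve-out from criterion (d). 15.7 does not say its list is exclusive, and it defers to an ICEC charter still to be written. All AEs are imported into the adjudication system, and important increases in chronic pulmonary medications are an AESI (15.1.5), so some dose increases could surface there. This stands as far as it goes: the documents do not support a claim that a dose increase can never reach the ICEC. But no passage routes such increases to a TTCW decision, and Table 4 would not read the answer.

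**The SAP does not say it counts these rises without adjudication.** A reader might infer that from Table 4. The table supports less: its row is labelled as new treatment, gives no derivation for dose increases and names no ICEC input. Nor is there evidence of a deliberate departure, since the table of changes from the protocol in SAP 11.0 is empty.

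**The 10% threshold may already be the allowance for tolerance.** It does keep small intravenous and subcutaneous titration out, so it would be wrong to say that all routine titration enters TTCW. But 11.1.3.2 has no size limit, and the inhaled limb has no threshold.

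**Titration may be rare.** Inclusion criterion 3 requires stable dosing for 4 weeks before Screening, and 14.1 restricts changes. At 2–5% in Illustration B the loss is only about 2 to 7 points. This stands, and the power figures should not be quoted as properties of this trial.

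**The primary endpoint is untouched.** TTCW is tested only if 6MWD succeeds, equal titration in both arms does not inflate type I error, and Protocol 16 requires the SAP to be final before unblinding. All true. They limit the damage but do not settle which count is correct.

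**Conclusion.** The contradiction is in the current text and does not depend on any assumed rate. Followed as written, the SAP definition counts patients whom Protocol 11.1.3.2 says are not events, in the first gated secondary endpoint. It should be resolved before unblinding.

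The affected events are intravenous or subcutaneous rises above 10% and any inhaled increase, where the reason is tachyphylaxis. If these are equally frequent in both arms, the effect is dilution of the hazard ratio and loss of TTCW power. If they differ by arm, bias could run either way. How much power is lost cannot be established from the documents.

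A reader might also infer that every change in PAH therapy should be adjudicated. The documents do not support that: 11.1.3.2 covers prostanoids only, no passage sends ERA or PDE-5 changes to the ICEC, and 11.1.3.2 states no test of attribution to PAH worsening.

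**What to change.** 1. Carry the exclusion and the ICEC determination in 11.1.3.2 into Protocol 7.1.2(d) and 16.3.2(d), SAP Table 3 and SAP 7.4.1(iv), for prostanoid additions and increases only.
2. Add those prostanoid changes to the list in Protocol 15.7 and to the ICEC charter.
3. In SAP Table 4, take the prostanoid part of the PAH-treatment component from the Adjudication Module and leave ERA and PDE-5 changes on the CRF. State how a dose increase is derived, including the reference dose for the 10% comparison.
4. Prespecify a TTCW sensitivity analysis that counts every prostanoid increase meeting criterion (d), whatever the reason.
5. Reconcile Protocol 14.1 with 11.1.3.2 on when background PAH therapy may change. They contradict each other as written; no clinical rule is proposed here.

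The cost is wording in one protocol amendment, the ICEC charter and the SAP, plus one additional analysis. The committee already exists, and 11.1.3.2 already requires PAH therapy doses to be recorded. The added work is ICEC review of the prostanoid changes. No new visit or assessment is needed.
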